As with the intervention arm, if the participant wishes to continue to think aloud so long as it doesn't distract them from completing the task. Participants will be asked to enter their medication order for the patient within a 'test ward' on the Cerner Millennium Powerchart system.

Order of control vs intervention arm-

Each participant will be randomly assigned to begin with either the control arm or the intervention arm (Group 1 and Group 2, see Table 1). With an equal number of participants being in each group. A random team generator (https://www.randomlists.com/team-generator) will be used for randomisation (see Figure 1) and participants will be assigned their 'participant number' in the order of their participation in the study.

Table 1 - Order of study arms, Group 1 and Group 2

Group 1	Group 2		
Practice 1 (simple) RxConnect	Practice 1 (simple) RxConnect		
Practice 2 (complex) RxConnect	Practice 2 (complex) RxConnect		
Test scenario 1 Control	Test scenario 1 RxConnect		
Test scenario 2 Control	Test scenario 2 RxConnect		
Test scenario 3 Control	Test scenario 3 RxConnect		
Test scenario 4 RxConnect	Test scenario 4 Control		
Test scenario 5 RxConnect	Test scenario 5 Control		
Test scenario 6 RxConnect	Test scenario 6 Control		

Figure 1 Example of participants randomised into two groups

Group 1									
1 Participant 5	2 Participant 43	3 Participant 19	4 Participant 3	5 Participant 34	6 Participant 23				
7 Participant 30	8 Participant 27	9 Participant 21	10 Participant 22	11 Participant 7	12 Participant 1				
13 Participant 10	14 Participant 36	15 Participant 32	16 Participant 26	17 Participant 46	18 Participant 14				
19 Participant 33	20 Participant 31	21 Participant 29	22 Participant 15	23 Participant 47	24 Participant 11				
25 Participant 6									
Group 2									
1 Participant 12	2 Participant 28	- Destisinent OF							
		3 Participant 35	4 Participant 41	5 Participant 44	6 Participant 2				
7 Participant 40			4 Participant 4110 Participant 49						
	8 Participant 38	9 Participant 20		11 Participant 16	12 Participant 37				
13 Participant 39	8 Participant 38 14 Participant 18	9 Participant 2015 Participant 25	10 Participant 49	11 Participant 16 17 Participant 17	12 Participant 37 18 Participant 9				

Sample size

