A target of 30-50 participants is desirable for this descriptive exploratory mixed methods study. This number has been selected pragmatically to account for approximately 5 participants per day over 10 working days.

Sample size sufficient to calculate statistical significance will not be feasible, therefore a power calculation will not be required.

Data collection and management

Data collection

Data will be collected via audio-visual recording which will take place on the SimWard, Paterson Building, St Marys Hospital. A Scotia Medical Observation Training System (smots, Scotia UK, Edinburgh, UK), with two 3- axis, ceiling- mounted video cameras, and three mobile, high-definition cameras equipped with boom microphones, will be used. The cameras will be angles at the computer screen ann onto the workstation and will not take footage of participants faces. Participants will be asked to remove or cover any name badges that may identify them prior to recording commencing.

The researcher will also keep field notes to assist with later analysis of the observations and interviews. The interviews will be transcribed verbatim by the study researcher prior to thematic analysis.

Participant demographic information will be collected via a short 'demographic questionnaire' at the beginning of the user testing session. Nasa Task Load Index questionnaires will be complete by the participant after each of the intervention arms.

Data management

Physical copies of the consent forms and participant list with pseudonymised participant study numbers will be kept within a locked room with swipe card access to the floor of the department.

Audio-visual recordings of the observations and semi-structured interview (See Appendix 1 for a sample interview guide), psuedoanonymised data capture forms and interview transcripts will be stored on an encrypted hard drive and kept in a locked room with swipe card access to the floor of the department. Interview transcripts will use the participant's psuedoanonymous study code in place of their name.

Publication of study findings will not contain identifiable data, participants will be given a study code name and only referred to by their profession and speciality.

Data and all appropriate documentation will be stored for a minimum of 10 years after the completion of the study.

Duration of study

The duration of the study will be six months from the date of the first participant recruited.

Study outcome measures

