The following outcomes will be measured-

Primary outcome measure-

Number of prescribing errors per scenario

• Subcategorised as - Incorrect drug, dose, route, frequency or patient.

Secondary outcome measures-

- The magnitude of any dose errors (deviation from recommended dosing range)
- Time taken to prescribe each medication
- Prescribers perceived mental load per prescribing scenario
- Hierarchical task analysis
- Qualitative feedback from participants

Number and magnitude of prescribing errors

We define a prescribing error as any of the following errors:

- Incorrect prescribed dose: prescribed doses that deviate from the recommended dose in the BNF/ BNFc or local guideline by more than 10%.
 - If the recommended dose is a range, deviations will be calculated from the max/min
 of the range, whichever is closest to the user calculated dose. If there are multiple
 recommended dose options e.g., from the BNF and from local guidelines, the
 researcher will calculate deviations based on the most appropriate source for the
 indication. When all sources are deemed equally valid, the researcher will record
 the smallest deviation allowed.
 - Magnitude of dosing error will be calculated as a percentage deviation from the recommended dose.
- Incorrect prescribed route: a medication prescribed via a route that deviates from the recommended route for the medication and dose as per the BNF/BNFc or local guidelines.
- Incorrect prescribed frequency: a medication prescribed for a frequency that deviates from the recommended frequency or that accumulated to a total daily dose for the medication and dose as per the BNF/BNFc or local guidelines.
- Incorrect patient: a medication order issued to incorrect patient's electronic medication chart.

Time

The length of time for each prescribing scenario will be calculated from the time the participant begins to read the first scenario, and for subsequent scenarios from the time they complete one scenario and move onto the next.

Task load index

At the end of each scenario the user will be provided with an online NASA TLX (task load index) form to complete (8).

Hierarchical task analysis

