Hierarchical task analysis (HTA) will be conducted for each of scenario, a framework will be created apriori based on the anticipated task steps and previous research (9,10), however any additional steps will be added if observed during video analysis. HTA results for participants using RxConnect will be compared to their usual practise.

Qualitative interviews

Following completion of the user testing scenarios, the participant will be invited to take part in a short semi-structured interview regarding their experience of using RxConnect and other more generic questions regarding the use of digital dosing support and indication-based prescribing. (See Appendix 1 for a sample interview guide).

Statistics and data analysis

Sample size

A sample size of 30-50 participants is desirable for this descriptive exploratory mixed methods study. A sample size calculation is therefore not relevant for this study.

Statistical analysis

Categorical data (error counts) from the control arm and intervention arm will be compared using the chi-square test.

Continuous data (magnitude of error, time, task load) will be measured using Mann-Whitney test for non-parametric data.

Sub analysis will explore the effect of possible confounders will be measured using multivariate logistic regression, subject to effect size and sample size limitations.

Variables which may be accounted for include - group number, scenario number, prescribing scenario complexity, prescriber grade, prescriber speciality, control arm or intervention arm.

Hierarchical task analysis

Hierarchical task analysis will be conducted to provide an overview of the prescribing workflow for the control arm and intervention. Vulnerable process steps can be highlighted if they are associated with increased error or time taken when prescribing the scenarios, along with any feedback from participants during practice, observation or in the qualitative interview.

Thematic analysis

Thematic analysis will be conducted using data from throughout the observations and the qualitative interviews (11).

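### The primary outcome is an error count that can exceed one per order, but its chi-square test has no stated unit; if single errors are tabulated, the false-positive rate can rise

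*Combined protocol and SAP*

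**What the plan says.** In section 3, under Study outcome measures, the primary outcome is "Number of prescribing errors per scenario", followed by "Subcategorised as - Incorrect drug, dose, route, frequency or patient". The definitions open with "We define a prescribing error as any of the following errors" and then list the types. Nothing says that an order can be scored under only one type. The frequency definition also refers to the accumulated daily dose, so one misread regimen could be scored under both dose and frequency.

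Under Statistical analysis, the only test attached to this outcome is: "Categorical data (error counts) from the control arm and intervention arm will be compared using the chi-square test". The section does not give the layout of the table, the denominator, or a rule for an order with several errors. A conditional sub-analysis follows: "Sub analysis will explore the effect of possible confounders will be measured using multivariate logistic regression, subject to effect size and sample size limitations". The outcome of that model is not named.

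On design, every participant prescribes in both arms (Table 1), and the order groups are balanced: "With an equal number of participants being in each group".

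**The concern.** A chi-square test assumes that each entry in the table is an independent observation. A count of errors per order is not made of such entries. Errors in the same order often share a cause, such as a misread regimen or a wrong drug that brings a wrong dose with it. If the table holds single errors, the arm totals vary more than the test allows for, and small p-values come too often.

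Several tables would fit the present wording: errors over orders, errors over five opportunities per order, orders with any error, or orders grouped by number of errors. They give different p-values, and the choice could be made after the data are seen. The comparison carries the study's safety question, since the introduction sets out to confirm or refute that the tool is as safe as existing prescribing aids.

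**Working it through.** The plan gives no alpha, power, error rate or clustering, so there is no figure of its own to reproduce.

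**Inputs from the documents**
- 30 to 50 participants (Sample size).
- Six test scenarios per participant, three per arm (Table 1). Arm sizes are therefore 3 × 30 = 90 to 3 × 50 = 150 orders, taking one order per scenario.
- Five error types (Study outcome measures).

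**Assumptions**
- Two-sided nominal level of 5%.
- 15% of orders contain at least one error.
- Of those, 30% contain two errors. Variants: 15% contain two; or 20% contain two and 10% three.

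**Step 1: single errors tabulated, independent orders.** Let X be the number of errors in an order and m = E[X]. The true variance per order is E[X²] − m². The test assumes m(1 − m) if the denominator is orders, or m(1 − m/5) if it is orders × 5. With r = true variance / assumed variance, the true level is 2 × (1 − Φ(1.96/√r)).

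For the 30% case:
- m = 0.15 × (0.7 × 1 + 0.3 × 2) = 0.195
- E[X²] = 0.15 × (0.7 × 1 + 0.3 × 4) = 0.285
- True variance = 0.285 − 0.195² = 0.2470
- Orders: assumed 0.195 × 0.805 = 0.1570; r = 1.573; level 11.8%
- Orders × 5: assumed 0.195 × 0.961 = 0.1874; r = 1.318; level 8.8%

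| Errors per erroneous order | m | True variance | Level, orders | Level, orders × 5 |
|---|---|---|---|---|
| 15% two | 0.1725 | 0.1877 | 8.7% | 6.5% |
| 30% two | 0.195 | 0.2470 | 11.8% | 8.8% |
| 20% two, 10% three | 0.21 | 0.3159 | 15.5% | 11.8% |

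Simulation with 90 and 150 orders per arm agrees with the orders column to within about 0.3 points.

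**Step 2: the Table 1 crossover.** Each participant and each scenario contributes to both arms. Differences between participants and between scenarios therefore cancel from the arm contrast, but the unpaired test still counts them as noise. This pulls the level down. With 30 and 50 participants, 8,000 null trials per setting (Monte Carlo standard error √(0.05 × 0.95/8000) = 0.24 points) and assumed participant and scenario standard deviations of 0.5 to 0.7 on the probit scale:
- 30% with two: about 8 to 10% (orders) and 6 to 7% (orders × 5).
- 15% with two: about 5.5 to 7.5% and 4 to 5.5%.

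**Step 3: a second error model.** Here each of the five types occurs in 5% or 10% of orders, and a shared order effect induces the clustering (30 to 50 participants, 4,000 null trials per setting). Across the two error-level tables tried, errors among opportunities and error totals by arm, the level is 3.4 to 5.6% with no order effect, 4.1 to 6.8% with a weak one (SD 0.3), 9.4 to 12.4% with a moderate one (SD 0.7) and 16.2 to 19.4% with a strong one (SD 1.2). The inflation follows the clustering, which is unknown.

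**Step 4: the order as unit.** In the second model, any error per order gives 1.3 to 5.5%, and orders with 0, 1 or 2+ errors give 2.1 to 6.0%. In the 15% model under the crossover, any error per order gives about 2.5 to 3.5%. There is no material inflation; the unpaired test is conservative.

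**Step 5: a paired alternative.** Take each participant's total errors with the tool minus total with usual practice, average this difference within each order group, and test the mean of the two group averages. The level is 3.9 to 5.6% in every setting of the second model.

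**The case against.** A reader might infer that the planned test inflates the false-positive rate outright. The text does not support that, because it never says that single errors are tabulated. With the order as unit the level stays near or below 5%. This part of the objection stands, and the inflation is conditional.

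A reader might also infer that chi-square is wrong for anything but a yes/no outcome. It is not: a table of orders with 0, 1 or 2+ errors by arm is a valid layout that treats counts as categories. Nor does the logistic model add a second source of inflation. It is a conditional look at confounders with no named outcome, and a binary response such as any error would collapse the count.

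Finally, the study is presented as exploratory: "A target of 30-50 participants is desirable for this descriptive exploratory mixed methods study", and "Sample size sufficient to calculate statistical significance will not be feasible, therefore a power calculation will not be required". No alpha is set, so no stated error rate is breached. This lowers the weight of the point. It does not remove it, because a p-value for the primary outcome is still planned and will be read.

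The opening of the error definition could be taken to mean one yes/no per order. That reading conflicts with the outcome itself, which is a number per scenario, and with the primary objective, which also concerns the number of errors.

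**Conclusion.** The point holds as a gap with a conditional consequence. The plan's only test of the primary outcome is assigned to a count that can exceed one per order, with neither the unit of analysis nor the handling of several errors defined. If single errors are tabulated, a nominal 5% test runs at about 9 to 12% with independent orders and about 6 to 10% in the crossover, given 15% of orders in error and 30% of those with two. With 15% holding two, little inflation is left in the crossover. With the order as unit there is none, and ignoring the pairing makes the test conservative. All error rates, clustering and random-effect sizes are assumptions. The point should be fixed before analysis, but in an exploratory study without a stated alpha it is not critical.

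**What to change.** State that chi-square will not be applied to summed error counts, and choose one of two analyses in advance:

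- **(a)** Test whether the order contains at least one prescribing error (yes/no), with a method that respects the pairing within participant, such as a logistic model with a participant effect. This also gives the logistic sub-analysis a defined response.
- **(b)** Keep the count, and compare each participant's total errors between arms with a paired comparison adjusted for order group (simulated level about 4 to 5.5%).

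In either case, report total errors and the five subtypes by arm descriptively.

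The cost is wording only; the scoring sheet does not change. Under (a), an order with several errors weighs the same as an order with one, although the counts are still reported. Option (b) stays closer to the stated objective.

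Two related items should be settled at the same time. Incorrect drug is listed as a subtype but has no definition in the list that follows. Table 1 shows six test scenarios while the session procedure in Appendix 2 says four; these must be reconciled, because they set the number of orders analysed.

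### The planned tests pool over scenario and participant although Table 1 is a balanced crossover, so the arm comparison of time and task load is unbiased but conservative and loses power

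*Combined protocol and SAP*

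**What the plan says.** Section 3, Statistical analysis, names one test per type of outcome. For errors: "Categorical data (error counts) from the control arm and intervention arm will be compared using the chi-square test". For the rest: "Continuous data (magnitude of error, time, task load) will be measured using Mann-Whitney test for non-parametric data". Possible confounders are left to a sub-analysis that "will be measured using multivariate logistic regression, subject to effect size and sample size limitations". Scenario number, scenario complexity and group number appear only in its list of variables that may be included.

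Table 1 ("Order of study arms, Group 1 and Group 2") sets the layout. Group 1 does scenarios 1-3 as control (the first row reads "Test scenario 1 Control") and 4-6 with RxConnect. Group 2 does the reverse. Assignment is random, "With an equal number of participants being in each group". Scenario order is fixed.

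On size, Section 3 says: "A target of 30-50 participants is desirable for this descriptive exploratory mixed methods study". It states that no power calculation is required.

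**The concern.** No participant does the same scenario in both arms, but every scenario is done in both arms by randomised groups. Scenario is therefore a factor that the design balances, and because the order is fixed it also carries period. The stated tests do not use it. The sub-analysis that could use it is conditional and logistic, so as written it does not reach time or task load.

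Scenarios can be expected to differ. The control-arm description has simple tasks followed by complex ones, and the briefing in Appendix 2 says that the scenarios may vary in complexity. The hypothesis in Section 1 that RxConnect is quicker and easier rests on time and task load. A test that counts scenario and participant differences as random error could miss a real effect at 30-50 participants.

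**Working it through.** **Plan's own figure.** There is no power, alpha, SD or effect size to reproduce. The only arithmetic is "approximately 5 participants per day over 10 working days": 5 × 10 = 50, the top of the range. The lower limit of 30 is not derived. With three scenarios per arm, 30-50 participants give 90-150 values per arm.

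**Assumed inputs (none is in the documents; log-time scale).** Residual SD 0.4 (variance 0.16); participant SD 0.3 (variance 0.09); scenarios within a set at −0.2, 0 and 0.2 (range 0.4, variance 0.08/3 = 0.0267). The second set is longer by D = 0, 0.2 or 0.4, that is 0%, 22% or 49%, which adds D²/4 = 0, 0.01 or 0.04. The true reduction is 15%, so the effect is −ln 0.85 = 0.1625. Groups are equal, each scenario value is one observation, and the test is two-sided at 5%.

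**Step 1: the estimate.** Each participant gives three values to each arm, so the participant effect cancels. Each scenario is done equally often in each arm, so scenario difficulty cancels. The true SE of the mean arm difference is √(2 × 0.16/(3n)), which is 0.0596 at n = 30 whatever D is. There is no bias.

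**Step 2: the reference distribution.** A test that treats all values as exchangeable uses √(2V/(3n)), where V is the variance it leaves in. At n = 30:
- Pooled, D = 0: V = 0.16 + 0.09 + 0.0267 = 0.2767, SE 0.0784.
- Pooled, D = 0.4: V = 0.3167, SE 0.0839.
- Stratified by scenario only: V = 0.25, SE 0.0745.
- Participant and set removed: V = 0.16, SE 0.0596.

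**Step 3: consequence.** Approximate power is Φ((0.1625 − 1.96 × reference SE)/0.0596):
- Pooled, D = 0: Φ((0.1625 − 0.1537)/0.0596) = Φ(0.15) = 56%.
- Pooled, D = 0.4: Φ((0.1625 − 0.1644)/0.0596) = Φ(−0.03) = 49%.
- Stratified: Φ((0.1625 − 0.1461)/0.0596) = Φ(0.28) = 61%.
- Both removed: Φ((0.1625 − 0.1168)/0.0596) = Φ(0.77) = 78%.

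Under no effect, the pooled test with D = 0 rejects with probability 2(1 − Φ(0.1537/0.0596)) = 2(1 − Φ(2.58)), about 1% instead of 5%.

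**Step 4: simulation with the rank tests themselves.** These run a little below the approximation, as expected.

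| n | Second set longer by | Pooled Mann-Whitney | Stratified by scenario | Participant and set adjusted | Gain from scenario alone | Further gain |
|---|---|---|---|---|---|---|
| 30 | 0% | 55% | 58% | 72% | 3 | 14 |
| 30 | 22% | 52% | 57% | 73% | 5 | 16 |
| 30 | 49% | 44% | 54% | 72% | 10 | 18 |
| 50 | 0% | 80% | 82% | 91% | 2 | 9 |
| 50 | 22% | 78% | 82% | 92% | 4 | 10 |
| 50 | 49% | 72% | 81% | 91% | 9 | 10 |

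The stratified test does not see D, so the drift from 58% to 54% is simulation error: with 1,500 runs the standard error near 50% is √(0.25/1500) = 1.3 points.

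**Step 5: larger scenario differences.** In a separate simulation with no participant variance and an effect of 0.35 within-scenario SD, let s be the scenario share of total variance. At n = 30, pooled power is 62%, 53%, 39% and 22% for s = 0, 0.2, 0.4 and 0.6, against 61-63% stratified. At n = 50 it is 84%, 78%, 66% and 45%, against 83-84%. In Step 4, s was 0.0267/0.2767 = 10% at D = 0 and 0.0667/0.3167 = 21% at D = 0.4.

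**The case against.** The strongest reply is that the study calls itself descriptive and exploratory and disclaims power, so lost power on secondary outcomes breaks no stated target. That stands. But the plan still specifies hypothesis tests, and Section 1 aims to prove or disprove the hypothesis, so avoidable loss of precision matters.

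A second reply is that scenario is already listed as a covariate. This holds in part: logistic regression can serve errors. It remains optional there and does not extend to time or task load.

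Third, the loss depends on variances that nobody has stated. That is correct. If scenarios did not differ, ignoring them would cost nothing.

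A reader might infer three stronger things that the documents do not support:
- **That scenario difficulty biases the arm comparison or produces false positives.** With equal groups it cancels, and the test errs on the cautious side. Only unequal groups would let a small part through.
- **That the whole gap to the fully adjusted test (17 to 28 points at n = 30) is due to scenario.** Even with no difference between sets the gap is 17 points, mostly from participant. The split does depend on order: scenario gains more once participant has been removed.
- **That the primary error comparison suffers a loss of known size.** The same structure is ignored there, but none of these calculations covers errors.

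**Conclusion.** The point holds as a matter of efficiency. The planned tests set aside the structure that Table 1 randomises. The result for time and task load is an unbiased but conservative comparison, with about 1% rejection under no effect in the assumed setting. Stratifying by scenario alone would recover about 2-10 points of power over 30-50 participants. Using participant as well brings the total to 11-19 points at n = 50 and 17-28 at n = 30. These sizes rest on the assumed SDs, a 15% effect, equal groups and per-scenario analysis, and would grow if scenarios differ more. The consequence is imprecise exploratory results, not a missed sample-size target.

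**What to change.** Replace the pooled tests with an analysis that follows Table 1:
- **Log time and task load:** a linear mixed model with arm and scenario (one level per test scenario, which also carries period) as fixed effects and participant as a random effect.
- **If a rank test is preferred:** take each participant's mean over scenarios 4-6 minus the mean over 1-3, and compare Group 1 with Group 2 by Mann-Whitney.
- **Errors:** stratify or adjust the arm comparison by scenario as part of the main analysis, not as an option.

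Do not simply switch to a paired test that ignores scenario, because each paired difference then carries plus or minus the set difference. At n = 30, under the same assumptions, a paired Wilcoxon test has about 60% power with the second set 22% longer and about 25% with it 49% longer, against 72-73% adjusted. It matches the adjusted test only when the sets are equally hard.

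Two inconsistencies need settling first. Table 1 has six test scenarios, while Appendix 2 step 8 has four, without saying whether in total or per arm. The task load form is completed after each arm under Data collection, but after each scenario under Task load index and in Appendix 2 step 9. If task load is recorded only once per arm, use the rank comparison of set differences.

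The cost is analysis wording and these two clarifications. No extra participants are needed, and time is already recorded per scenario.
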